8.2.2 Assessment of Secondary Outcomes (Baseline and end of study)

Secondary outcomes are patient-related outcomes are:

- generic functional performance measured by the “Functional independence measurement” (FIM)
- specific functional assessments of the upper AND/OR lower extremity
- Stroke impact scale (SIS)
- Upper extremity:
 - Fugl-Meyer test
 - Box and Block test
- Lower extremity:
 - Functional ambulation categories (FAC)
 - Comfortable walking speed (10m Walk test= TMT)
 - Chedoke-McMaster Stroke Assessment Measure (CMSA), the walking index
 - Berg Balance scale (BBS)
- Health-related quality of life (EQ-5D)

Patient-related outcomes will be assessed after the last training session. These outcomes will be assessed at baseline and at the end of the intervention by raters observing the patient during aforementioned tests. During final assessment, raters will be kept blind to the baseline values.

Cost elements and structures for cost description analysis

- quantities and prices of inputs (staff, technologies, infrastructure)
- intensity of use of new rehabilitation technologies
 - h/day, h/week, time of the day
- description of operational procedures

- patient(device)/therapist ratio
- identification of main drivers for increasing efficiency
- efficiency gains
- current reimbursement
 - future reimbursement possibilities and models

Secondary outcomes will be assessed at baseline and at the end of the intervention by raters observing the patient during aforementioned tests. During final assessment, raters will be kept blind to the baseline values.

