6.4 Criteria for Withdrawal/ Discontinuation of Participants

Patients not willing to adhere to the protocol will not be included. For included patients who, while having already attended some session but are not able to complete the six weeks program within the intensity planned, a tailored reduction of intensity in terms of days, hours per days and/or sessions per day is considered. A maximum training break of 7 days is foreseen

Patients who withdraw before the start of the study will be replaced.

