7 STUDY INTERVENTION

7.1 General Information

7.1.1 Study Intervention

- Series of tailored rehabilitative training with the use of new technology which provide feedback and allow for a targeted and intensive and dense training.
- With supervision based on patients preconditions and therapy device (e.g. patient/therapist ratio= 3/1).
- A training series lasts four weeks and comprises 3-5 training-days per week. Maximum training break of 7 days. Five sessions of training with duration of 45 min per session, and up to four hours each day are foreseen.
- The training can take place in an outpatient or inpatient setting.
- Training will be organized in individual one-to-one or group sessions.

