8.2.4 Assessments in Participants who prematurely Stop the Study

Project investigators at each site will contact patient who withdrew from the study. Patients will be asked for reasons of withdrawal

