8.3.4 End of study

After the intervention will end, and patient-related outcomes will be obtained either by self-report or measured by an observer.

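### The functional end assessment follows the last training session with no planned date, and patients who stop early have no described end assessment, so the pre-post change describes mainly those who tolerated training

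*Combined protocol and SAP*

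**What the plan says.** The functional and quality-of-life battery (FIM, SIS, Fugl-Meyer, Box and Block, the gait and balance tests, EQ-5D) is taken twice. For the second occasion, section 8.2.2 says "Patient-related outcomes will be assessed after the last training session" and then "These outcomes will be assessed at baseline and at the end of the intervention by raters observing the patient during aforementioned tests". Section 8.3.4 says "After the intervention will end, and patient-related outcomes will be obtained either by self-report or measured by an observer". None of these gives a study day, a week or a window.

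For patients who stop prematurely, the only data collection in 8.2.4 is "Patients will be asked for reasons of withdrawal". Section 7.4 rules out follow-up but also commits to analysing every included patient.

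On length and interruptions, 7.1.1 says "A training series lasts four weeks and comprises 3-5 training-days per week", whereas 6.4 refers to patients who "are not able to complete the six weeks program within the intensity planned". Section 6.4 also says "A maximum training break of 7 days is foreseen" and allows a reduction in days, daily hours or daily sessions. Section 7.3 has patient and therapist draw up the training plan beforehand, covering every scheduled day.

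Section 10.3.2 plans univariate pre-post tests. Section 10.4 limits the secondary analysis to participants whose training break was seven days or less.

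**The concern.** When a patient's last session falls depends on how well the patient tolerated the programme, and adherence is the trial's primary interest. The date of one outcome is therefore set by another. The greater difficulty is with patients who stop. The plan does not say that they are tested at the planned end, and it does not clearly say that they are tested at all.

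Functional change is a named secondary objective (4.3), and 4.1 wants functional data as an input to later socioeconomic calculations. If the patients who could not sustain the training contribute no end value, the change reported as typical of the programme comes from a selected group. With five patients per site, differences in how sites handle a stopper would be visible in the results.

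**Working it through.** **1. The plan's own figure.** 4 sites × 5 patients = 20, which agrees with section 10. No power, effect size or dropout rate is stated, so no sample-size calculation bears on this point.

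**2. What happens to each type of patient, reading the sections together.**

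| Patient | Governing text | End value |
|---|---|---|
| Completes without a break | 8.2.2, 8.3.4 | After the last session, at the planned end |
| Break of up to 7 days, not made up | 6.4, 7.1.1, 8.2.2 | At the planned end |
| Break of up to 7 days, made up | 6.4, 8.2.2 (make-up not mentioned) | Up to one week later |
| Stops early, site follows 8.2.4 and 7.4 | Reasons asked, no follow-up | None |
| Stops early, site reads 8.2.2 literally | Test after whatever session was last | At a time set by the stop |

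The last two rows are both open to a site, and neither gives a value comparable with the others.

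**3. Interval among patients with breaks of at most 7 days.** Count from the first session, five training days a week, with day 1 the first day of week 1. The gap from baseline to first session is not specified and is left out. Last session day = 7 × (weeks − 1) + 5.

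- Four weeks, no break: 7 × 3 + 5 = day 26.
- Four weeks, 7-day break made up: 26 + 7 = day 33. Ratio 33/26 = 1.27, a difference of one week.
- Four weeks, 7-day break not made up: day 26, a difference of 0.

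This takes the 7 days as a total. The documents do not say whether the limit is per break or in total. Fewer hours or sessions per day leave the date unchanged. A reduction in days would move it only if a fixed total of training days had to be delivered, which is not stated.

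**4. Programme length.** Under the six-week wording the last session is at 7 × 5 + 5 = day 40, and 40 − 26 = 14 days. The contradiction between 7.1.1 and 6.4 moves the planned end by twice as much as a made-up break does.

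**5. Missing end values.** Let k patients stop without an end assessment (k is assumed; no rate is given). The share with a pre-post change is (20 − k)/20:

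- k = 1: 19/20 = 95%
- k = 2: 18/20 = 90%
- k = 4: 16/20 = 80%

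Each such patient is 1/20 = 5% of the sample and 1/5 = 20% of a site. They would not be a random subset, because stopping training is what removes them.

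**The case against.** Much of the case on the other side stands.

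- *The design cannot separate recovery from training anyway.* Correct. Section 5.1 says effectiveness is not yet under study and there is no control group. A common date makes elapsed time equal across patients, but it leaves background recovery inside every change score. The aim concerned is secondary.
- *A break need not move the end date.* Also correct. If the series is four calendar weeks planned in advance, the adherence-driven spread among non-stoppers is zero.
- *Sections 10.4 and 7.3 may remove stoppers from the secondary analysis.* Only in part. The filter in 10.4 concerns breaks and does not name stoppers, 7.3 excludes those who cannot meet a minimum programme, and 7.4 says that everyone is analysed. Even if stoppers are removed, the selection remains.
- *The flow diagram in 8.1 could not be read.* It might show a visit day, so the point is limited to the readable text.
- *Testing after training fits an objective about response to training.* It does, and a planned date may fall before make-up sessions are finished. That is a real cost of the change.

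A reader might infer a more than six-fold spread in the interval, from day 5 for a patient who stops after week 1 to day 33 (33/5 = 6.6). The documents do not support this. The short end needs a functional test at the stop, which 8.2.4 does not describe, and the long end needs make-up sessions, which no section provides for. A reader might also convert the interval into scale points per week. The documents contain no recovery rate, and one rate cannot apply to FIM, walking speed, block counts, ambulation categories and EQ-5D, which have different units.

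**Conclusion.** The point holds for missing or mistimed end values in patients who stop. The text gives them either no functional end assessment or one at an adherence-dependent time, so the secondary pre-post change describes mainly patients who tolerated the programme. The size depends on the number of stoppers, at 5% of the sample each.

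For patients with breaks of at most 7 days the timing effect is at most about one week (about 26 versus 33 days). It arises only if missed days are made up and the 7-day limit is a total; otherwise it is zero. The primary feasibility outcome and N = 20 are unaffected.

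**What to change.** 1. Reconcile the four-week series in 7.1.1 with the six-week programme in 6.4. The planned end date depends on it.
2. In 8.2.2 and 8.3.4, schedule the end assessment at the end date of the patient's advance training plan (7.3), within a stated window, whether training was paused, reduced or stopped.
3. In 8.2.4, invite patients who stop training but keep consent to that same assessment, with the self-report scales by telephone if they cannot attend. Adjust 7.4 to match.
4. In 10.3.2 and 10.4, report functional change for all assessed patients beside the set with breaks of seven days or less, and show the baseline-to-end interval with both.

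The date is already fixed by the training plan, and the battery and raters are those in use, so the change is mostly wording. It costs one visit or call for each of the few patients who stop, and some assessments may fall before make-up sessions, if there are any, are finished.

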8.2.3 Assessment of Safety Outcomes

8.2.3.1 Serious Adverse Events

Recording of serious adverse event (SAE) information, what information needs to be collected: time of onset, duration, resolution, action to be taken, assessment of intensity, relationship with study treatment; refer to Section 9 for SAE definition and procedures; define specific process to ask the participant at the visits about adverse events, collection of spontaneous reports.

8.2.3.2 Laboratory Parameters

NA

8.2.3.3 Vital Signs

Patient self-perceived effort during each training session as expressed by a VAS will be recorded.

8.2.4 Assessments in Participants who prematurely Stop the Study

Project investigators at each site will contact patient who withdrew from the study. Patients will be asked for reasons of withdrawal

8.3 Procedures at each training day

At each training day, the participant and responsible physiotherapist will plan the program of the day according to the **training plan (CRF page 53)**. During each training bloc a physiotherapist will supervise the patient. Intervention-related outcomes will be completed after or during each training bloc and at the end of each training day.

8.3.1 Screening Visit

During the screening procedure, eligibility criteria will be checked by study personnel at each clinic and informed consent will be obtained.

8.3.2 Baseline Visit

During the initial visit, **patient related outcomes** will be obtained. For every patient a trainings- and intervention plan (CRF page 53ff) will be established.

8.3.3 Start of training

In the beginning of each training day, patient and therapist will plan the day including sessions, and devices to be used.

8.3.4 End of study

After the intervention will end, and patient-related outcomes will be obtained either by self-report or measured by an observer.

9 SAFETY

During the entire duration of the study, all serious adverse events (SAEs) that may be causally related to the study intervention are collected and documented in source documents. Reportable events are recorded in the case report form (CRF). Study duration encompassed the time from when the participant signs the informed consent until the last protocol-specific procedure has been completed, including a safety follow-up period.

9.2 Recording and Assessment of Serious Adverse Events

The investigator has the responsibility for SAE identification, documentation, and assessing the causal relationship study intervention.

All SAEs will be fully documented in the appropriate CRF. For each SAE, the investigator will provide the onset, duration, treatment required, outcome and action taken with regard to the study intervention.

The assessment by the investigator with regard to the study intervention relation is done according to the following definitions:

Unrelated	
• The event started in no temporal relationship to the medical intervention applied and• The event can be definitely explained by underlying diseases or other situations.
Related	
• The event started in a plausible temporal relationship to the medical intervention applied and• The event cannot be definitely explained by underlying diseases or other situations.

9.3 Reporting of Serious Adverse Events

If, in the course of a clinical trial, serious adverse events occur in participants in Switzerland, and it cannot be excluded that the events are attributable to the intervention under investigation, the investigator must report these events:

- to the sponsor **within 24 hours** after they become known; and
- to the CEC **within 15 days**.

Safety and protective measures

If immediate safety and protective measures have to be taken during the conduct of this clinical trial, the investigator must notify the CEC of these measures, and of the circumstances necessitating them, **within 7 days**.

Annual Safety Report

All SAEs will be summed up in the **annual safety report (ASR)** and submitted to the CEC. ASR shall contain:

- A summary of events including severity and causal relationship to the intervention and on the safety of participants.
- The accompanying letter provided with the Annual Safety Report should contain a short summary of the status of the clinical trial in Switzerland (number of centers open/closed, number of patients recruited/recruitment closed, and number of SAEs).

9.4 Follow up of (Serious) Adverse Events

Participants terminating the study (either regularly or prematurely) with

- reported ongoing SAE, or
- any ongoing AEs of laboratory values or of vital signs being beyond the alert limit will return for a follow-up investigation. This visit will take place up to 30 days after terminating the treatment period. Follow-up information on the outcome will be recorded on the respective SAE page in the CRF.

Follow-up investigations may also be necessary according to the investigator's medical judgment even if the participant has no SAE at the end of the study. However, information related to these investigations does not have to be documented in the CRF but must be noted in the source documents.

10 STATISTICAL METHODS

10.1 Hypothesis

Not applicable, as this study is a feasibility study. **Determination of Sample Size**

Twenty patients, five at each site are planned to be enrolled. A sample size calculation is not applicable for this feasibility study.

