4.5 Primary Outcome

The primary outcome is to assess the feasibility of planned trainings. Every training and training day will be described in terms of

- devices used,
- duration of training,
- training mode (passive, active or resistive) and
- feedback given by the device.

The specific interest is the adherence of the patients:

- to planned trainings in terms of planned vs. actually performed training-days and training intensity.

- the subjectively perceived effort by the patients to perform the trainings will be recorded on a visual analogue scale (VAS).
- the subjectively perceived effectiveness will be recorded by using the “Patients Global Impression of Change” = PGICS)

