6 STUDY POPULATION

Four rehabilitation centres located across the German speaking area of Switzerland will participate in this project.

Klinik Lengg, Zurich

The Klinik Lengg has a workload of 250-stroke patients a year. All patients fulfilling the inclusion criteria will be asked for participation.

Reha Rheinfelden

The Reha Rheinfelden has a workload of approximately 400 ischaemic and haemorrhagic stroke patients as in-and outpatients a year, which will be recruited via direct contact, clinic's database, and flyer distributed in-house.

Kliniken Valens

Kliniken Valens treated approximately 460 ischaemic and 150 haemorrhagic stroke inpatients a year, who will be approached by a research assistant to check their eligibility while entering the clinical site for inpatient rehabilitation.

Rehaklinik Zihlschlacht

The Rehaklinik Zihlschlacht has a yearly workload of approximately 300 stroke patients; some of them will be treated after discharge in the clinic's outpatient setting. Study personnel will approach patients regarded eligible for further evaluation.

Each site aims to include five patients leading to 20 patients in total. Study sites are entering the study consecutively and according to their personnel capacity.

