10.3.1 Primary Analysis

Intervention-related outcomes: Absolute and relative frequency together with parameters of central tendency and spread will be derived for any devices used, duration of intervention per day, per session, per device. This applies analogously for training and feedback modes used and for self-perceived exertion rates. Adherence rates will be examined by using Chi-Square statistics.

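### The primary analysis gives the main feasibility result, adherence in 20 patients, no estimate of its uncertainty; it relies on an unspecified Chi-square test

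*Combined protocol and SAP*

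**What the plan says.** Sections 10.1 and 10.2 (run together in the text) fix the size: "Twenty patients, five at each site are planned to be enrolled". On the hypothesis they say "Not applicable, as this study is a feasibility study", and on the size "A sample size calculation is not applicable for this feasibility study". No expected adherence rate, SD or target precision is given.

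Sections 4.5 and 8.2.1 make feasibility the primary outcome and single out adherence "to planned trainings in terms of planned vs. actually performed training-days and training intensity". They set no cut-off that would class a patient as adherent.

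Section 10.3.1 has two parts. For devices and durations, "Absolute and relative frequency together with parameters of central tendency and spread will be derived", and the same treatment is extended to training mode, feedback mode and perceived exertion. Adherence gets its own sentence: "Adherence rates will be examined by using Chi-Square statistics". Section 10.3 describes the analysis of intervention-related outcomes as mainly descriptive. Section 10.4 puts all patients in the primary analysis. No confidence interval, or interval of any other kind, appears in the available text.

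**The concern.** A feasibility study does not need a power calculation, but its main figure should come with a measure of how far it could be off. Spread does not do that: an SD or range shows how much patients differ, not how well 20 of them locate the average.

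The Chi-square sentence does not fill the gap. It does not say what is compared with what, against which rate, or whether the unit is the patient, the day or the session. Set against planned counts, performed counts are not an independent sample, because performed trainings are a subset of planned ones. Run on session records, the test would treat many records from one patient as if they came from different patients.

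Feasibility is the primary objective (section 4.2), and section 4.1 wants first insight into data for socioeconomic cost calculations. A reader using the adherence figure for that purpose needs to see what range of values the 20 patients are compatible with.

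**Working it through.** **The plan's own figure.** Four sites (section 6) × 5 patients = 20. This reproduces, but only as a count: with no rate, SD, confidence level or power stated, there is no formula to check. The 95% two-sided level below is an assumption.

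**Mean adherence per patient** (closest to the measure the protocol names). Half-width = t(0.975; 19) × SD / √20 = 2.093 × SD / 4.472 = 0.468 × SD. The SD is assumed.

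| Assumed SD (points) | 95% half-width (points) |
|---|---|
| 10 | 4.7 |
| 20 | 9.4 |
| 30 | 14.0 |

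A half-width of 20 points would need an SD of 20 / 0.468, about 43 points.

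**Yes/no result per patient** (not defined in the protocol; shown for scale). Clopper-Pearson: the lower limit is the 2.5% quantile of Beta(x, n − x + 1), and the upper limit is the 97.5% quantile of Beta(x + 1, n − x), with n = 20.

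| Result | Exact 95% interval | Distance below / above |
|---|---|---|
| 15/20 = 75% | 50.9% to 91.3% | 24.1 / 16.3 |
| 16/20 = 80% | 56.3% to 94.3% | 23.7 / 14.3 |
| 18/20 = 90% | 68.3% to 98.8% | 21.7 / 8.8 |
| 20/20 = 100% | 83.2% to 100% | 16.8 / 0 |

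**Pooling days or sessions.** Section 7.1.1 gives 4 weeks × 3 to 5 days = 12 to 20 days per patient and, at five sessions a day, 60 to 100 sessions per patient, or 1,200 to 2,000 over 20 patients. (Section 6.4 speaks of six weeks. The two passages must be reconciled, but the argument does not depend on which is meant.)

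- Sessions treated as independent, 80% adherence: 1.96 × √(0.16 / 1,200) = 2.3 points and 1.96 × √(0.16 / 2,000) = 1.8 points, so about 2.
- Training days, with design effect 1 + (m − 1) × ICC, m = 12 to 20, and an assumed within-patient ICC, at 80%: about 4 to 5 points at ICC 0, about 10 at ICC 0.3, and 17.5 at ICC 1.

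The choice of unit alone can therefore move the apparent half-width several-fold, and section 10.3.1 does not name the unit.

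**Chi-square across clinics.** If the test compared a yes/no result between the four clinics, each clinic would have five patients. The two expected counts per clinic sum to 5, so at any overall rate strictly between 0% and 100% both are below 5, where the usual large-sample approximation is doubtful.

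**Grouping in clinics.** Design effect = 1 + (5 − 1) × ICC. For an assumed clinic ICC of 0.05 to 0.20 this is 1.2 to 1.8, so 20 patients carry the information of 20 / 1.2 = 16.7 down to 20 / 1.8 = 11.1.

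**The case against.** The plan is modest about its claims: single arm, descriptive, a first insight, effectiveness explicitly left for later. If the count or the mean and SD are reported with n, a reader can work out an approximate interval. No threshold for acceptable feasibility is set, so an interval would have nothing to be tested against. All of this is fair. It makes the point a matter of reporting and method rather than a flaw in the design, and the missing threshold is a separate gap that an interval does not close. It does not justify the Chi-square sentence, which is the only stated analysis of adherence and, as written, cannot be carried out in one definite way.

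Stronger readings are tempting and should be resisted:

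- A reader might infer that the feasibility figure is uncertain by about 20 points either way. That needs a yes/no patient-level rate of roughly 50% to 80%, which the protocol never defines. Above that range the interval is clearly asymmetric, and for mean adherence the half-width is probably smaller.
- A reader might infer that the result will be over-interpreted. That is a prediction the documents neither support nor refute.
- A reader might infer that sessions will be pooled as independent. The plan does not say so; it only leaves this open.
- A reader might infer that more patients are needed. Nothing here shows that.

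**Conclusion.** The point holds in this form: the primary analysis leaves the main feasibility result without an estimate of its uncertainty, and the one method named for adherence does not supply it. The absence is plain from section 10.3.1; the missing precision statement in section 10.2 is secondary.

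The size is conditional. It is about 5 to 14 points either side for mean patient adherence if the SD is 10 to 30 points. If a yes/no patient-level result is also reported, an observed 80% would run from 56% to 94%. Both assume 95% confidence, all 20 patients analysed, and patients independent of one another; grouping by clinic may make both optimistic. The change is worth making because it costs almost nothing and bears on the primary outcome.

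**What to change.** Keep n = 20. In section 10.3.1, replace the Chi-square sentence with text along these lines: for each enrolled patient, the number of training days performed is divided by the number planned, and likewise for training intensity, with its measure stated; these values are summarised over all enrolled patients as a mean with a t or bootstrap 95% interval, the patient being the unit.

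Then add:

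- Any patient-level proportion for adherence or completion is given with a Clopper-Pearson 95% interval.
- If days or sessions are pooled, the interval allows for clustering by patient.
- Grouping in four clinics may make the intervals optimistic.
- Device-use and mode frequencies stay purely descriptive; device choice depends on the patient's goal, the impaired limb and local availability, so intervals there would add little.

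Section 7.3 excludes patients who do not meet the minimum programme. The text should confirm that they remain in this denominator, as section 10.4 implies. In section 10.2, one sentence can state the expected precision with its assumptions, using the figures above.

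The cost is a few sentences and trivial analysis, with no change to enrolment, treatment or data collection. The downside is that the stated certainty becomes less favourable.
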